1. PROTOCOL SUMMARY

1.1. Synopsis

Open-label Long-Term Extension Study for Participants With Treatment-Resistant Major Depressive Disorder Who are Continuing Esketamine Nasal Spray Treatment From Study 54135419TRD3013

Open-label Extension Study to Assess Long-term Safety of Esketamine Nasal Spray

Esketamine hydrochloride (HCl) is referred to as JNJ-54135419-AAC. Esketamine is a nonselective, noncompetitive antagonist of the N-methyl-D-aspartate receptor (NMDAR), an ionotropic glutamate receptor. Through NMDAR antagonism, esketamine produces a transient increase in glutamate release leading to increases in α-amino-3-hydroxy-5-methyl-4-isoxazole propionic acid receptor (AMPAR) stimulation and subsequently to increases in neurotrophic signaling that restore synaptic function in these mood regulatory brain regions. Esketamine nasal spray is indicated for use in combination with a selective serotonin reuptake inhibitor (SSRI)/ serotonin-norepinephrine reuptake inhibitor (SNRI) to treat adults with treatment-resistant major depressive disorder (MDD). Esketamine nasal spray has also been approved by the United States Food and Drug Administration for MDD with acute suicidal ideation or behavior.

OBJECTIVES AND ENDPOINTS

Primary

Objectives

Primary	
To assess the long-term safety and tolerability of esketamine nasal spray in combination with an SSRI/SNRI in participants who have completed 32 weeks of esketamine nasal spray treatment in Study TRD3013.	Intervention-emergent adverse events (AEs), including intervention-emergent AEs of special interest Suicidal ideation and behavior: Columbia-Suicide Severity Rating Scale (C-SSRS)
Secondary	

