5.3.2. Estimand for treatment-emergent adverse events

Primary Trial Objective: To assess the long-term safety and tolerability of esketamine nasal spray in combination with an SSRI/SNRI in participants who have completed 32 weeks of esketamine nasal spray treatment in Study 54135419TRD3013.

Estimand Scientific Question of Interest: What is the safety and tolerability of esketamine nasal spray in combination with an SSRI/SNRI in participants who have completed 32 weeks of esketamine nasal spray treatment in Study 54135419TRD3013, based on the development of treatment-emergent adverse events (AEs)?

The estimand is defined by the following 5 components:

Study Intervention: esketamine nasal spray in combination with an SSRI/SNRI

Population: participants who have completed 32 weeks of esketamine nasal spray treatment in Study 54135419TRD3013 and received at least one dose of esketamine in Study 54135419TRD4010

Variable: development of treatment-emergent AE: from the initial administration of study intervention in Study 54135419TRD3013 through the day of last dose in Study 54135419TRD4010 plus 30 days

Summary Measure: number and incidence of subjects who develop an treatment-emergent AE per person-time at risk

Intercurrent events and their corresponding strategies:

	Name of Strategy for Addressing Intercurrent
Intercurrent Events	Events and Its Description
	While on treatment: All AEs occurring through
intervention for any reason	the day of last dose plus 30 days are included in
	analysis
Withdrawal from the study	While on treatment: Same as above

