If the onset date of an adverse event is missing both day and month, it will be set to the earliest of:

- i) January 1 of the year of onset, as long as this date is after the initial dosing date of Study 54135419TRD3013.
- ii) one day after initial dosing date in Study 54135419TRD3013, if this date is the same year that the AE occurred.

A completely missing onset date of an adverse event will be set to the initial dosing date in Study 54135419TRD3013.

If the end date of an AE that is not recorded as ongoing is missing completely or partially, following imputation rule will be applied:

- For AEs with outcome Fatal, the AE end date is the death date
- The missing day of resolution of an adverse event will be set to the last day of the month of resolution.
- If the resolution date of an adverse event is missing both day and month, it will be set to the earlier of the date of withdrawal, study completion, or December 31 of the year.
- A completely missing resolution date of an adverse event that is not recorded as ongoing will be set to the date of study completion/discontinuation.

For a total number of participants with treatment-emergent AEs, SAEs,... (not on SOC, PT level), the 95% confidence interval of the proportion and incidence rate will be calculated. For proportion, the 95% Clopper-Pearson confidence interval will be calculated. The 95% confidence interval of the incidence rate will be based on a Poisson model with development of treatment-emergent AE as dependent variable, an intercept and log (time at risk) as offset.

Summary tables will be provided for treatment-emergent AEs:

- AEs
- AEs (SOC, PT level only for most common TEAE) stratified by AE duration
- End date same as start date
- End date later than start date (ongoing AEs to be classified in this group)
- Serious AEs (SAEs)
- AEs leading to discontinuation of each study agent within the study intervention
- AEs by severity
- AEs by relationship to each study agent within the study intervention
- AEs leading to dose interruption/dose modification of each study agent within the study intervention.

In addition to the summary tables, listings will be provided for participants who:

- Had SAEs
- Had AEs leading to discontinuation of study intervention.
- AEs of special interest (Appendix 7)

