Incidence of treatment-emergent AEs of special interest will be summarized, grouped in the following MedDRA-based categories: sedation, dissociation, suicidality, suggestive of abuse potential, cystitis and hepatic impairment. See Appendix 7 for a list of AEs in each category.

CONFIDENTIAL – FOIA Exemptions Apply in U.S.

A listing of participants who died will be provided.

Duration of TEAE

Additionally a bar chart will be created to present the duration of AEs (Treatment-emergent AEs in more than 5% of patients).

Duration of AEs will be calculated as:

- If AE start date = AE end date: AE end time AE start time
- If AE start date < AE end date: AE end date AE start date +1
- Note: for AE with outcome FATAL: AE end date= death date

AEs are categorized in following categories

- Duration: <= 1hour
- Duration: > 1 hour to <= 2 hours
- Duration: > 2 hours to <= 3 hours
- Duration: > 3 hours to <= 8 hours
- Duration: > 8 hours but AE start date=AE end date
- Unknown: Missing duration (ie. missing start or end time) and AE start date=AE end date
- Duration: 2 days to <= 7 days
- Duration: 8 days to <=28 days
- Duration: >28 days or AE ongoing

Bar chart that shows the percentage of AEs in each category is created.

Clinically significant weight change

- Calculate the number and % of patients with an increase of at least 7% in body weight at any point in time compared to baseline. Only include visits until last dose + 14 days.
- Calculate the number and % of patients with a decrease of at least 7% in body weight at any point in time compared to baseline. Only include visits until last dose + 14 days.
- Above proportions are calculated on all patients in the safety analysis set who have baseline and at least one post-baseline body weight measurement.
- If body weight missing, assume no 7% increase/decrease from baseline.

Medication

- Calculate the number and % of patients who received any concomitant therapy for TEAE. Denominator is patients in safety analysis set with at least one TEAE.
- Calculate the number and % of patients who received any concomitant therapy for TEAE, by preferred term. Denominator is patients in safety analysis set who developed the specific preferred term as TEAE.

• Analyses are based on data on AE page (AECONTRT). If AECONTRT is missing, assume no concomitant therapy received.

Days with AE

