5.7.6.1. Healthcare Resource Use Questionnaire (HRUQ)

5.7.7. Other Variables and/or Parameters

5.7.7.1. Definition

5.7.7.2. Analysis Method

5.7.8. Definition of Subgroups

The primary and secondary endpoints will be analyzed as described in the respective sections for the following subgroups.

Subgroup	Variant	Definition
Sex		Male
		Female
Age Group		Adult [18-64]
		Elderly [>=65]
Number of previous		2
treatment failures		>=3
Class of continued oral AD		SNRI
at baseline		SSRI
Race		White
		Other
Region		Africa
		Asia Pacific
		Europe
		South America

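### The interval for the adverse-event incidence rate rests on a Poisson model with no stated limit type and no zero-event rule; exact Poisson limits would cover low counts

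*SAP*

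**What the plan says.** SAP section 5.3.2 gives the summary measure of the primary adverse-event estimand as "number and incidence of subjects who develop an treatment-emergent AE per person-time at risk". Section 5.3.2.1.1 defines the rate as participants with at least one event divided by time at risk. The clock starts at the first dose in the parent study. It stops at the first event or, without an event, 30 days after the last dose.

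Intervals are planned for participant totals such as TEAEs and SAEs: "not on SOC, PT level), the 95% confidence interval of the proportion and incidence rate will be calculated". The two measures are handled differently:

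- Proportion: "For proportion, the 95% Clopper-Pearson confidence interval will be calculated".
- Rate: "The 95% confidence interval of the incidence rate will be based on a Poisson model with development of treatment-emergent AE as dependent variable", with "an intercept and log (time at risk) as offset".

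The type of limit for the rate is not stated, and nothing is said about rows with no events. Section 5.7.8 then carries the method over: "The primary and secondary endpoints will be analyzed as described in the respective sections for the following subgroups". These include the elderly and four regions, with no minimum size or event count. Section 3 expects 100 to 200 participants in all.

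**The concern.** An intercept-only Poisson model with a log-time offset estimates the log of the rate. With no events that estimate is minus infinity, so the interval most software prints by default cannot be computed. With a handful of events the default interval is symmetric on the log scale, while the Poisson distribution at such counts is not.

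The study has no control arm and no hypothesis, so its safety result consists of estimates and their intervals. For a row with no events, the upper limit is the whole content of that row. If the SAP does not fix the limit type, the programmer chooses it, possibly after seeing the counts, and the candidate choices differ materially at low counts.

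**Working it through.** **Inputs from the SAP**
- Model: intercept plus log(time at risk) offset (5.3.2.1.1). The log link is inferred from the offset. The 95% interval is taken as two-sided.
- Expected enrolment: 100 to 200 (section 3).
- Follow-up: 32 weeks in the parent study (5.3.2), up to 104 weeks in the extension (1.2), plus 30 days (5.3.2.1.1).

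**Assumed, because the documents give no figure**
- Event counts of 0 to 3.
- A subgroup of 20.
- Full follow-up for everyone.

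The plan states no interval or event count, so there is no figure of its own to reproduce.

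**Formulas**, for x participants with the event and T person-years at risk:
- Wald: (x/T)·exp(±1.96/√x), since the standard error of the log rate is 1/√x.
- Profile likelihood: the values where the log-likelihood falls 3.841/2 = 1.92 below its maximum.
- Exact (Garwood): χ²(0.025; 2x)/(2T) to χ²(0.975; 2x+2)/(2T), with lower limit 0 when x = 0.

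**Limits on the count (divide by T for the rate)**

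| Events | Wald | Profile likelihood | Exact |
|---|---|---|---|
| 0 | none | 0 to 1.92 | 0 to 3.69 |
| 1 | 0.141 to 7.10 | 0.057 to 4.40 | 0.025 to 5.57 |
| 2 | 0.500 to 8.00 | 0.333 to 6.18 | 0.242 to 7.22 |
| 3 | 0.968 to 9.30 | 0.746 to 7.78 | 0.619 to 8.77 |
| 10 | 5.38 to 18.59 | 5.01 to 17.54 | 4.80 to 18.39 |

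Fitting the model itself confirmed the Wald column. With 100 participants and one event it returned 0.05 to 2.64 per 100 person-years, which is 0.141 and 7.10 divided by 268.9. With no events the fit failed, at both 100 and 20 participants.

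**Zero events.** 1.92/3.69 = 0.52, so the profile-likelihood upper limit is about half the exact one.

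**One to three events, Wald against exact**
- Lower limit: 5.6, 2.1 and 1.6 times too high.
- Upper limit: 7.10/5.57, 8.00/7.22 and 9.30/8.77, that is 27%, 11% and 6% too high.
- At 10 events the upper limits agree to about 1%.

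**On the rate scale.** Maximum time at risk per person is (136 × 7 + 30)/365.25 = 982/365.25 = 2.69 years. At zero events the exact upper limit is:
- N = 100: T = 268.9, so 3.69/268.9 = 1.37 per 100 person-years (profile likelihood 0.71).
- N = 200: T = 537.7, so 0.69 per 100 person-years.
- Subgroup of 20: T = 53.8, so 6.9 per 100 person-years.

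Earlier stopping shortens T and raises these limits in proportion.

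**How often zero occurs**, from (1 − risk)^n with assumed risks: at N = 100 and 1% risk, 37%; at N = 100 and 2%, 13%; in a subgroup of 20 at 5%, 36%.

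**Coverage at an expected count of 2.** The chance of no event is 13.5%. When there is an event, the Wald interval covers 94% of the time, and every miss comes from a lower limit that is too high. Counting the zero-event data sets as having no interval, the figure is 81%. Profile likelihood covers 85% and exact 98%.

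**The case against.** A reader might infer that rare harms and small subgroups are left with no usable bound at all. The documents do not support that. The same paragraph gives every such row an exact interval for the proportion, and that interval exists at zero events: the upper limit is 3.62% for 0/100, 1.83% for 0/200 and 16.8% for 0/20. Only the person-time version lacks a settled limit.

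A reader might also infer that the plan prescribes Wald limits, or that it would understate risk at one to three events. Wald is not named. If it were used, its upper limit would be too high rather than too low, and the anti-conservative error would sit in the lower limit. Most of the 81% coverage figure restates the zero-event gap.

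Nor can the failure be assumed to fall on adverse events of special interest. The protocol synopsis places them in the primary endpoint ("Intervention-emergent adverse events (AEs), including intervention-emergent AEs of special interest"), but the SAP says only: "Incidence of treatment-emergent AEs of special interest will be summarized, grouped in the following MedDRA-based categories". If no interval is planned there, the method cannot fail there. If they fall under the open-ended list of totals, they already have the exact interval for the proportion. Asking for an explicit interval in those rows is a separate reporting request. Events at SOC or preferred-term level have no interval by design.

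Finally, the study tests nothing, and SAEs, AEs leading to discontinuation and deaths are listed individually, so low counts will be visible case by case.

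All of this stands, and it limits the scope and severity. It leaves the rate without a defined or reliable interval at zero events, and the rate is the estimand's stated summary measure.

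**Conclusion.** The point holds for the person-time rate only. Followed as written, the model gives either no limit at zero events or, under profile likelihood, an upper limit about half the exact one. At one to three events the default Wald interval is shifted upward at both ends. The exposed rows are low-count totals such as SAEs, especially within the section 5.7.8 subgroups. The row for any TEAE is likely to have many events and is unlikely to be affected.

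The comparison of limits on the count needs no assumption about the trial. The rates of 1.37 and 6.9 per 100 person-years assume full follow-up, and the latter also assumes a subgroup of 20. How often such rows will occur depends on risks and subgroup sizes that the documents do not give. Severity is minor, because the study is descriptive and no decision rule uses this interval.

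**What to change.** In SAP section 5.3.2.1.1, replace the model-based interval with the exact Poisson (Garwood) interval at all counts:

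- lower limit χ²(0.025; 2x)/(2T), set to 0 when x = 0;
- upper limit χ²(0.975; 2x+2)/(2T).

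Using it at every count avoids a switch of method that depends on the data, and it matches the exact choice already made for the proportion. Section 5.7.8 inherits the change. Section 5.4.1.2 uses the same model for the relapse endpoint, so the same sentence could be carried there for consistency.

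The cost is one SAP sentence and a closed-form calculation, with no new data. The downside is that exact limits are slightly conservative: about 98% coverage at expected counts of 1 to 2 and 99% at 3.

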- For each patient, calculate the number of days on which the patient had any TEAE, including only days from date of first dose of study intervention until date of last dose of study intervention inclusive. If at a certain day the patient had multiple TEAEs, this should be counted as one day. Report summary statistics (mean, SD, median, range).
- Divide the number calculated above by study intervention duration (date of last dose of study intervention date of first dose of study intervention +1). Report summary statistics (mean, SD, median, range).
- For AEs that are ongoing (AEENRF=AFTER): AE end date will be set as date of study completion/discontinuation

TEAEs that led to dose reduction

- Calculate percentage of TEAEs that led to dose reduction: denominator is all TEAEs. Numerator is all TEAEs with action 'Dose Reduced' (AEACNS1/AEACNS2).
- Calculate percentage of TEAEs that led to dose reduction, by PT: denominator is all TEAEs
 of specific PT. Numerator is all TEAEs of specific PT with action 'Dose Reduced'
 (AEACNS1/AEACNS2).

TEAEs on dosing days

- Calculate percentage of TEAEs that occurred on dosing days, in total and on PT level
- Of TEAEs that occurred on dosing days, calculate the percentage with same day resolution, in total and on PT level.

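### The AE-duration chart gives any event that crosses midnight at least 2 days, whatever its length in hours, and its top bar pools ongoing events with events known to exceed 28 days

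*SAP*

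**What the plan says.** SAP Section 5.3.2.1.1, under the heading on TEAE duration, plans a bar chart for treatment-emergent AEs seen in more than 5% of patients. Duration is computed in one of two ways:

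- Same date: "If AE start date = AE end date: AE end time AE start time".
- Different dates: "If AE start date < AE end date: AE end date AE start date +1".

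The minus signs are missing from the text I worked from. I read both rules as end minus start and make nothing of the omission.

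Same-date events go into hour classes, the longest being "Duration: > 8 hours but AE start date=AE end date", or into an unknown class if a time is missing. The first class open to an event with different dates is "Duration: 2 days to <= 7 days". The last class is "Duration: >28 days or AE ongoing". The output is described as follows: "Bar chart that shows the percentage of AEs in each category is created".

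Further on in the same section, the analysis of days with an AE closes ongoing events differently: "AE end date will be set as date of study completion/discontinuation".

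**The concern.** The hour classes show that the chart is meant to resolve duration finely within the first day. The rule drops that resolution for any event whose end falls on the next calendar date. Such an event jumps from an hour class to a multi-day class, however brief it was, so the bars are not always in order of true duration. The reader cannot see this from the labels.

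The top bar raises a different question. It sets no minimum observed time for an ongoing event. An event that began a few days before last contact shares a bar with events known to have lasted more than 28 days, and the percentage shown cannot be split.

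What is at stake is one descriptive picture. Protocol Section 2.2.3.4 reports that most earlier AEs came soon after dosing and were gone the same day, and this chart bears on whether that pattern holds over longer treatment.

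**Working it through.** The plan states no figure to reproduce. The check applies the SAP rules to example events and then asks how many events could be affected.

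**Midnight rule.** With different dates, duration in days = end date − start date + 1. The smallest date difference is 1, so the minimum is 1 + 1 = 2 days.

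| Start | Elapsed time | Dates | Class under the SAP |
|---|---|---|---|
| 10:00 | 1 h | same | up to 1 hour |
| 23:30 | 1 h | next day | 2 to 7 days |
| 23:00 | 2 h | next day | 2 to 7 days |
| 20:00 | 8 h | next day | 2 to 7 days |
| 01:00 | 22 h | same | over 8 hours, same date |

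Rows 2 and 5 show the reversal: 1 hour is placed above 22 hours.

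The inclusive count also acts at the longer cut-points. An event of 6.01 elapsed days that starts at 23:54 has a date difference of 7 and scores 8, so it enters the 8-to-28-day class. One of 27.01 elapsed days with the same start time scores 28 + 1 = 29 and enters the top class. These shifts are small relative to the durations involved. At the one-day boundary an hour becomes 2 days.

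**How often midnight is crossed.** The documents give no onset-time distribution. If onset were uniform over 24 hours (an assumption), P(cross) = d/24 for an event of d hours:

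- 1 h: 1/24 = 4.2%
- 2 h: 2/24 = 8.3%
- 3 h: 3/24 = 12.5%
- 8 h: 8/24 = 33%

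For short events after daytime dosing the chance is near 0. Dosing takes place at the site under supervision (Protocol Section 6.4).

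**Ongoing events.** Protocol Section 8.3.1 collects AEs until the 2-week safety follow-up visit, and the Schedule of Activities allows ±2 days. A non-serious event that starts after the last dose and is still open at that visit has therefore been observed for at most about 14 + 2 = 16 days. Under the SAP it goes to the top bar. By comparison, an event ongoing after 3 observed days is in the top bar, while one that ended at that point would score 3 + 1 = 4 days and fall in the 2-to-7-day class.

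An event that is open at the end of observation and whose true duration is 28 days or less must have started in the last 28 days. With onset uniform over T observed days (an assumption), such events are at most 28/T of all AEs. T counts 32 weeks of the parent study, the time in this study, and 2 weeks of follow-up:

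| Time in this study | T | Upper bound 28/T |
|---|---|---|
| 104 weeks | (32 + 104 + 2) × 7 = 966 days | 2.9% |
| 26 weeks | (32 + 26 + 2) × 7 = 420 days | 6.7% |
| almost none | (32 + 0 + 2) × 7 = 238 days | 11.8% |

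These are upper bounds under one onset assumption, not estimates.

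**The case against.** The strongest defence is that this is a stated and consistent date convention. Inclusive day counting is also used for the duration of study intervention. The split between same-date and later-date events also runs through the section: the table stratified by AE duration, the same-day resolution percentages, and the repeats in the supplementary analysis. On that view, an event present on two calendar dates counts as 2 days. This stands as a description of the convention. It does not answer the reversal on a chart that otherwise sorts by the hour, and no label warns of it.

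Three stronger readings are tempting, and the documents do not support them.

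- A reader might infer that the chart assigns ongoing events a duration of more than 28 days. It does not. The label names ongoing events, and their true duration is censored, so nothing known is being overstated. What remains is pooling. The defence can add that grouping ongoing events with the longest ones is conservative for safety reporting and matches the stratified table, where ongoing events go with those ending on a later date.
- A reader might infer that the rule for days with an AE gives the same record a second, conflicting duration. That analysis counts calendar days per patient between first and last dose, with overlapping events merged, and needs a closing date to do so. It is a different quantity for a different output.
- A reader might infer that misplaced records make up much of the 2-to-7-day or top bar. No figure in the documents supports this, and supervised dosing with mostly same-day resolution points the other way for midnight crossing.

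It is also fair to say that recording of end times for next-day resolutions is not confirmed. Even same-date events have a class for missing times.

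**Conclusion.** The point holds in a limited form. The duration rule misorders events that cross midnight: each is shown as at least 2 days regardless of elapsed hours, and nothing else in the SAP corrects this. The pooling of ongoing events in the top bar is disclosed by its label, so it costs information but does not misstate anything.

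The number of affected events is unknown and probably small. The percentages above rest on uniform onset. Only one descriptive chart is touched. AE counts, proportions and incidence rates, which carry the primary safety analysis, are unaffected. This is a desirable refinement and not a threat to any conclusion.

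**What to change.** Two changes to the duration text in SAP Section 5.3.2.1.1:

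1. Where start and end times are both recorded and the event ends on the next calendar day, classify it by elapsed hours. Replace the same-date class for more than 8 hours with a class for more than 8 to 24 hours that serves same-date and next-day events alike. Keep next-day events longer than 24 hours in the 2-to-7-day class. This last rule is needed because a next-day event can run well past 24 hours: 01:00 to 23:00 the following day is 46 hours. When a time is missing, keep the date rule.
2. Give ongoing events their own bar, labelled as ongoing at last contact, and reserve the top duration class for events known to exceed 28 days.

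The cost is a few lines of SAP wording and minor programming. The second change needs no new data. The first works only if end times are recorded for next-day resolutions; if they are not, a footnote saying that any event crossing midnight is shown as at least 2 days would give the reader the necessary warning. After the first change the hour bars no longer correspond to the same-date stratum of the table by AE duration, so the chart should note that too.
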